7.2 Rationale and Discussion of Study Design

Snakebite envenoming represents a deadly and unmet global medical need. While antivenoms comprise the SOC for treatment of snakebites, they suffer from several limitations including specificity of each antivenom for specific species of snake, limited access to antivenom in rural areas, practical storage requirements, and delays in administration. Treatment of snakebite envenoming with the small-molecule drug varespladib-methyl, which targets sPLA₂ present in approximately 95% of snake venoms, has the potential to overcome several limitations of serum-based antivenoms that underpin traditional SOC.

The proposed study in the United States and India will provide coverage of a broad spectrum of venomous snake genera, including elapids, vipers, and pit vipers in differing geographies and differing sPLA₂ structures. Study sites will be selected based on demonstrated historical incidence of snake bites from species deemed relevant to this study, to ensure a broad range of envenoming toxins are expected to be encountered in potential study subjects.

This study was designed to exclude as few critically ill subjects as possible. The primary criteria for participation are that subjects must be ≥ 5 years of age, must present with an initial SSS of (A) 2 points in any SSS category other than GI or Renal and 1 or more additional point in any other SSS category other than GI or Renal or (B) an initial SSS score of ≥ 3 in any SSS category other than GI or Renal, must not be pregnant or breast-feeding, are not taking excluded medications, and have not been previously administered antivenom at another facility.

The study design allows for both treatment arms (varespladib-methyl and placebo) to receive SOC (e.g., antivenom) concurrently. Thus, critically ill adult and pediatric subjects may receive emergency treatment in a timely manner while being evaluated for the potential clinical benefit associated with inhibition of venom sPLA₂ by varespladib-methyl.

Because subjects with severe snakebites are admitted to emergency departments, this study was designed to screen, enroll, and administer treatment in a single visit at the hospital upon admission. Because varespladib-methyl is administered orally, subjects who demonstrate substantial improvement and are eligible for discharge from the hospital may continue investigational product (IP) treatment in an outpatient setting.

Ophirex, Inc.
OPX-PR-01

Risks associated with the control (placebo) arm of this study include the same risks associated with SOC (antivenom).

The efficacy endpoints for this study were selected to evaluate if varespladib-methyl plus SOC is superior to SOC alone. The primary endpoint was selected to evaluate clear clinical benefit based on SSS, whereas secondary and exploratory endpoints were selected to evaluate improvements in each subject's snakebite severity and QoL over the course of treatment. PK analysis will be performed at specified timepoints throughout the treatment period, including in pediatric subjects enrolled.

7.3 Selection of Doses in the Study

LY333013 (varespladib-methyl) is formulated in an immediate-release film-coated oval tablet at a unit dosage strength of 250 mg for oral administration. Ophirex is developing varespladib-methyl (LY333013) for oral administration for 7 days total for the treatment of venomous snakebites. LY333013 is a prodrug that is rapidly metabolized to LY315920; LY315920 is a potent inhibitor of sPLA₂ in vitro and in vivo.

This study evaluates the safety, tolerability, and efficacy of varespladib-methyl in subjects bitten by venomous snakes from diverse regions and snake genera, including (but not limited to) pit vipers (e.g., rattlesnake, copperhead), vipers (e.g., Russell's viper and saw-scaled viper), and elapids (e.g., coral snake, cobra, krait).

The proposed dosing of varespladib-methyl for adult subjects consists of an initial loading dose of 500 mg ($2 \times 250 \text{ mg}$ oral tablet) varespladib-methyl upon randomization, followed by dosing with 250 mg varespladib-methyl ($1 \times 250 \text{ mg}$ oral tablet) approximately 12 hours later, followed by BID dosing with $1 \times 250 \text{ mg}$ varespladib-methyl oral tablets for the remainder of the 7-day treatment period.

Pediatric subjects (ages 5 to < 18) will be administered doses of varespladib-methyl determined by allometric scaling, provided as 50 mg capsules, depending on age. Pediatric doses were determined based on the 250 mg BID adult dose. Median weights from the Centers for Disease Control (CDC) growth charts were used for the allometric scaling, with weights averaged for male and female pediatric subjects. Subjects 5 to < 11 years old will receive an initial loading dose of 200 mg varespladib-methyl, an additional dose of 100 mg approximately 12 hours later, followed by 100 mg BID. Subjects 11 to < 18 years old will receive a loading dose of 400 mg varespladib-methyl, an additional dose of 200 mg approximately 12 hours later, followed by 200 mg BID. Including the loading dose, subjects will receive a total of 14 doses of study medication. Dosing may occur on 7 or 8 calendar days, depending on whether the first dose of study medication is in the morning or the afternoon.

Initial loading dose may be taken with or without food to accommodate the need to provide treatment as soon as possible following enrollment. The status of food consumption at the time of administration of the initial loading dose should be recorded in the case report form (CRF). All scheduled doses following the initial dose should be taken with food for the remainder of the study's BID dosing period.

A summary of formulations and dosing for adult (age \geq 18 years) and pediatric (ages \geq 5 to < 18 years) subjects is provided in Table 3.

Table 3 Summary of Adult and Pediatric Dosing

	$Age \ge 18 \text{ yr (Adult)}$	Age 11 to < 18 yr	Age 5 to < 11 yr
Oral Formulation	Tablet	Capsule	Capsule
Loading Dose	500 mg	400 mg	200 mg
	(2 x 250 mg)	$(8 \times 50 \text{ mg})$	(4 x 50 mg)
Second Dose	250 mg	200 mg	100 mg
(approximately 12 hours	(1 x 250 mg)	$(4 \times 50 \text{ mg})$	(2 x 50 mg)
after loading dose)			
BID Dose (for remainder	250 mg	200 mg	100 mg
of 7-day treatment	(1 x 250 mg)	$(4 \times 50 \text{ mg})$	(2 x 50 mg)
period)			

Abbreviations: BID = twice daily; yr = year

7.4 Study Sites

The study will take place at approximately 10 to 20 sites in the United States and India. Each site is anticipated to screen enough subjects to randomize approximately 5 to 20 subjects. No stratification or selection for type of snakebite will be made. Study site activation and enrollment periods will be planned to allow maximum enrollment during the most active seasonal snakebite months in each region. A study site with a high recruitment rate may be allowed to recruit more subjects if other sites have slow enrollment.

7.5 End of Study Definition

The EOS is the date when the last subject's last study visit occurs.

8 STUDY POPULATION

8.1 Selection of Study Population

Investigators or their designees will maintain a screening log of all candidates who are considered for participation in this study, including reasons for ineligibility or refusal to participate. Consent, screening, randomization, and dosing will occur on the same day. Subjects who do not meet all the eligibility criteria will not be enrolled. This study is estimated to enroll and randomize 110 male and female subjects equally into 2 groups. At least 94 evaluable subjects are expected to be available, allowing for up to 15% loss to follow-up.

8.2 Study Entry Criteria

8.2.1 Inclusion Criteria

A subject will be eligible for study participation if he or she meets all the following criteria:

- 1. Is a male or female \geq 5 years of age with venomous snakebite.
- 2. Index event (snakebite) must be symptomatic and symptom onset must have occurred within 10 hours of eligibility assessment.
- 3. Patients must meet one of two categories of inclusion criteria:

Category 1: The patient has not yet completed first dose of antivenom:

SSS inclusion score* of ≥ 2 in one system and ≥ 1 in another system (2+1) **OR** ≥ 3 in at least one system.

OR

Category 2: The patient has completed an initial dose of antivenom:

SSS inclusion score* of ≥ 2 in one system and ≥ 1 in another system (2+1) OR ≥ 3 in at least one system **AND** CGI-I score of ≥ 5 (i.e., minimally worse, much worse, or very much worse).

- 4. Is willing (or legally authorized representative is willing) to provide informed consent prior to initiation of any study procedures.
- * Only local wound, pulmonary, cardiovascular, hematologic, or nervous system scores qualify for SSS inclusion criteria. GI and Renal scores are not used for inclusion. Hematologic score may be counted if available, but inclusion should not wait for laboratory results. Point of care tests (e.g., 20WBCT) may be used for enrollment, if used per site standard of care (see Appendix A).

8.2.2 Exclusion Criteria

A subject will be excluded from the study if he or she meets any of the following criteria:

OPX-PR-01

1. Is considered by the Investigator to have a clinically significant upper GI bleed evidenced by significant hematemesis, "coffee-ground" emesis or nasogastric aspirate, hematochezia thought to originate from upper GI tract.

- 2. Has history of CVA or intracranial bleeding of any kind, acute coronary syndrome, MI, or severe pulmonary hypertension.
- 3. Has known history of inherited bleeding or coagulation disorder.
- 4. Is, at Screening Visit, using the following anticoagulants: warfarin/coumadin, argatroban, bilvalirudin, lepirudin, apixaban, dabigatran, clopidogrel, prasugrel, ticlodipine or another anticoagulant agent not specifically listed, or has used heparin, enoxaparin, fondaparinux, or other low molecular weight heparin or antiarrhythmic drugs within 14 days prior to treatment.
- 5. Has a history of chronic liver disease such as chronic active viral hepatitis, alcohol-related liver disease, non-alcoholic steatohepatitis, non-alcoholic fatty liver disease, hemochromatosis, primary biliary cirrhosis, primary sclerosing cholangitis, autoimmune hepatitis.
- 6. Reports or has known pre-existing renal impairment or chronic kidney disease.
- 7. Has a known allergy or significant adverse reaction to varespladib-methyl.
- 8. Is considered by the Investigator to be unable to comply with protocol requirements due to geographic considerations, psychiatric disorders, or other compliance concerns.
- 9. Is pregnant, has a positive serum human chorionic gonadotropin (hCG) pregnancy test or not willing to use a highly effective method of contraception for 14 days after initial treatment, or is breast-feeding.

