	warfarin/coumadin, argatroban, bilvalirudin, lepirudin, apixab dabigatran, clopidogrel, prasugrel, ticlodipine or another anticoagulant agent not specifically listed, or has used heparin enoxaparin, fondaparinux, or other low molecular weight hepa					

	5. Has a history of chronic liver disease such as chronic active viral hepatitis, alcohol-related liver disease, non-alcoholic steatohepatitis, non-alcoholic fatty liver disease, hemochromatosis, primary biliary cirrhosis, primary sclerosing cholangitis, autoimmune hepatitis.						
	6. Reports or has known pre-existing renal impairment or chronic kidney disease.						
	7. Has a known allergy or significant adverse reaction to varespladib-methyl.						
	8. Is considered by the Investigator to be unable to comply with protocol requirements due to geographic considerations, psychiatric disorders, or other compliance concerns.						
	9. Is pregnant, has a positive urine or serum human chorionic gonadotropin (hCG) pregnancy test or not willing to use a highly effective method of contraception for 14 days after initial treatment, or is breast-feeding.						
Safety Follow-up Assessments	Follow-up schedule: Day 14 and Day 28 after first dose of varespladib-methyl. If discharged before Day 7, follow-up will also be performed on Day 3 (if discharge prior to Day 3) and Day 7.						
Study Duration	Approximately 12 months						
Sample Size	The sample size for this study was determined by a formal power calculation. The total enrollment for this study will be approximately 110 subjects (94 evaluable). The assumptions used to determine sample size are as follows:						
	• 2-sided alpha level 5%						
	 Power 85% Randomization Ratio 1:1. The randomization will be stratified by age group (5 to < 11 years, 11 to < 18 years, ≥ 18 years) and by the presence or absence of neurotoxicity (SSS nervous system subscore of 0–1 or ≥ 2) at Baseline, resulting in 6 strata in total Withdrawal rate of 15% 						
	 The sample size also assumes: A minimum difference of change in SSS average of the 6- and 9-hour scores of 1.1 and a standard deviation of 1.75 						
Statistical Analysis	Descriptive statistics (n, mean, median, standard deviation [SD], minimum, and maximum for continuous data; frequencies and percentages for categorical data) will be used to summarize study data and details of analysis are outlined in the study Statistical Analysis Plan.						

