11.3.2 Pregnancy

All subjects of childbearing potential who participate in the study should be counseled on the need to practice adequate birth control and on the importance of avoiding pregnancy during treatment. Subjects should be instructed to contact the Investigator or study staff immediately if pregnancy occurs or is suspected.

Participants of reproductive potential must agree to use a highly effective method of contraception from the time of consent and for 14 days following his or her last dose of IP. Highly effective methods of contraception are as follows:

- combined (estrogen- and progestogen-containing) hormonal contraception associated with inhibition of ovulation (oral, intravaginal, or transdermal)
- progestogen-only hormonal contraception associated with inhibition of ovulation (oral, injectable, or implantable)
- intrauterine device, intrauterine hormone-releasing system
- bilateral tubal occlusion
- vasectomized partner
- sexual abstinence
- double-barrier method (condoms, sponge, diaphragm, with spermicidal jellies, or cream).

Confidential

Ophirex, Inc.
OPX-PR-01

Pregnancy testing will be conducted prior to administration of the IP on every subject of childbearing potential. A subject who is found to be pregnant at the Screening Visit will be excluded from the study and considered to be a screening failure.

A subject who becomes pregnant during IP treatment will be immediately discontinued from receiving the study drug. The Investigator must report the pregnancy within 72 hours of learning of the pregnancy, to the study CRO pharmacovigilance team using the Pregnancy Data Collection Form via the same fax number and/or email address as for SAE reporting. The Investigator should contact the designated individual(s) who receive SAE notification and record information related to the pregnancy on a pregnancy form provided by the sponsor or its designee.

The Investigator is also responsible for following the pregnancy until delivery or termination. These findings must be reported on a pregnancy form and forwarded to the designated individual(s). The event meets the SAE criterion only if it results in a spontaneous abortion or a congenital anomaly.

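### Exclusion criterion 9 asks for contraception for only 14 days from first treatment, about 6.5 days less than Section 11.3.2 requires after a full course

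*Protocol*

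**What the plan says.** Two places in the protocol list exclusion criterion 9. The one in Section 8.2.2 excludes a subject who is "not willing to use a highly effective method of contraception for 14 days after initial treatment". The synopsis (Section 2.1) uses the same period: "method of contraception for 14 days after initial treatment, or is breast-feeding". Both count from initial treatment.

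Section 11.3.2 (Pregnancy) counts from a different point. The undertaking it demands of those with reproductive potential reads: "use a highly effective method of contraception from the time of consent and for 14 days following his or her last dose of IP".

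On dosing, Section 7.3 says that "subjects will receive a total of 14 doses of study medication", with the second dose "approximately 12 hours later, followed by BID dosing with" a single tablet for adults. The synopsis gives the same total, as one loading dose and 13 further doses. Section 7.3 adds that dosing may fall on 7 or 8 calendar days. No section says how the two contraception periods relate or which one governs.

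**The concern.** The two periods have the same length but different starting points, and treatment lasts about a week, so they end about a week apart. The shorter one is in the eligibility list. Section 8.1 bars enrolment of anyone who does not meet all the criteria, and it puts consent, screening, randomization and dosing on one day. Criterion 9 is the only criterion that mentions contraception, so staff working from the list in an emergency department would ask about the shorter period.

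A subject willing to use contraception only until about day 14 would then be enrolled without having given the agreement in Section 11.3.2. What is at stake is a safety rule for participants of reproductive potential. Sample size, power and the efficacy analysis do not depend on it.

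There is also a sign that text elsewhere was not kept in step with the exclusion list. Section 8.4 refers to exclusion criteria 6, 7 or 10 for liver history, renal tests and pregnancy tests, but the list stops at 9 and those topics are now criteria 5, 6 and 9. This is suggestive only.

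**Working it through.** **Inputs**

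- Criterion 9 (Synopsis; Section 8.2.2): 14 days from initial treatment, read as the first dose. Section 10.1 uses the word the same way when it places the end of follow-up 28 days after the initial study intervention, made up of 7 days of treatment and about 21 more.
- Section 11.3.2: from consent until 14 days after the last dose.
- Section 7.3: 14 doses, taken here as exactly 12 hours apart.
- Section 8.1: consent and first dose on the same day, so the earlier start in Section 11.3.2 adds only hours.

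**The plan's own figure.** Twice daily for 7 days is 2 × 7 = 14 doses, which agrees with 1 loading dose + 13 further doses.

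**Time of the last dose.** After *k* doses, the last falls (*k* − 1) × 12 h after the first. For *k* = 14 this is 13 × 12 = 156 h = 6.5 days.

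**End of each period, counted from the first dose (full course)**

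- Criterion 9: 14 × 24 = 336 h = day 14.0.
- Section 11.3.2: 156 + 336 = 492 h = day 20.5.
- Gap: 20.5 − 14.0 = 6.5 days.

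The gap always equals the time from first to last dose, because both periods add the same 14 days.

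**Post-dose cover under criterion 9 (full course).** 14.0 − 6.5 = 7.5 days of the 14 required, and 7.5 / 14 = 54%.

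**Stopping early**

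| Doses taken | Last dose | Gap |
|---|---|---|
| 1 | 0 h | 0 days |
| 2 | 12 h | 0.5 days |
| 7 | 72 h | 3.0 days |
| 14 | 156 h | 6.5 days |

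**Calendar days.** A full course on 7 calendar days gives a gap of 6 days; on 8 calendar days, 7 days.

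**Pregnancy test.** The last serum test is at the Day 28 ± 3 visit (Section 10.2.3.11). The earliest is day 28 − 3 = 25, later than 20.5, so it falls after either period.

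**The case against.** The two rules can both be met. Section 11.3.2 is mandatory, criterion 9 does not say that 14 days from the first dose is sufficient, and a site that reads the whole protocol will obtain the longer agreement. Criterion 8 also lets the investigator exclude someone who will not comply with protocol requirements. The consent form was not available for this review and may already state the longer period. Finally, no harm is shown: both periods cover every scheduled dosing day of a full course and at least about 7.5 days beyond, the documents give no reproductive-risk figure for the disputed days, and Section 11.3.3, in discussing overdose, expects blood levels to fall quickly when hepatic and renal function are normal.

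Much of this stands, and it keeps the point minor. It does not remove the error. The agreement Section 11.3.2 demands has to be obtained at screening, and the criterion used there states too short a period. Criterion 8 is a matter of judgement and does not correct the wording.

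Two narrower objections are fair. The 6.5 days is nominal and not a strict ceiling: doses are only approximately 12 hours apart, and Section 11.2.2.3 allows IP to be interrupted, so late doses could lengthen the gap. And Section 11.3.2 is limited to participants of reproductive potential, a limit that criterion 9 lacks in a trial enrolling from age 5.

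**Conclusion.** The concern holds. Criterion 9 understates the contraception period that Section 11.3.2 requires, and nothing in the protocol corrects it. For a completed course the shortfall is nominally 6.5 days (6 or 7 in calendar days). It falls to 0 if only the loading dose is taken, and could run somewhat past 6.5 days if doses are delayed or interrupted.

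This rests on reading initial treatment as the first dose and on 12-hour spacing. If initial treatment were read as the whole course, the criterion would be ambiguous and would need the same edit. The point applies only to participants of reproductive potential. It is a minor internal inconsistency in an eligibility and safety rule.

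**What to change.** In criterion 9, in both the synopsis and Section 8.2.2, replace the period counted from initial treatment with the one in Section 11.3.2: from consent until 14 days after the last dose of IP. In the same edit, limit the contraception clause to participants of reproductive potential so that the sections agree fully. Check that the participant information states the same period.

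The text change is two sentences. No visit, test or analysis changes. Section 14.8 requires a formal amendment with investigator signature and IRB approval, and SAP Section 1 cites separate US (3.0) and India (3.1) protocol versions, so both should be checked. The edit could be carried in the next amendment made for other reasons, with sites told meanwhile to apply the Section 11.3.2 period, which satisfies both rules.

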8.3 Early Subject Withdrawal

All subjects are free to withdraw from participation in this study at any time, for any reason. The Investigator should make every reasonable attempt to keep subjects in the study; however, subjects must be withdrawn from the study if they withdraw consent to participate. Investigators must attempt to contact subjects who fail to attend scheduled visits by telephone or other means to capture any AEs and determine whether a subject should be withdrawn. Every possible attempt should be made to collect and report AEs upon withdrawal, as described in Section 11.2.

The sponsor reserves the right to withdraw a subject due to protocol deviations or other reasons.

If a subject is withdrawn before completing the study, the reason for withdrawal and the date of study discontinuation will be recorded on the appropriate page of the electronic case report form (eCRF). Whenever possible and reasonable, the evaluations that were to be conducted at the completion of the study should be performed at the time of withdrawal.

The reason for subject discontinuation from study medication or withdrawal from the study will be recorded on the eCRF. Subjects who sign the informed consent form and are randomized but do not receive the study intervention may be replaced. Subjects who sign the informed consent form, are randomized and receive the study intervention, and subsequently withdraw or are withdrawn or discontinued from the study will not be replaced.

8.4 Discontinuation of Study Intervention

An Investigator may discontinue a subject from study treatment for the following reasons:

- Pregnancy
- Significant study intervention or study procedure noncompliance
- If any clinical AE, laboratory abnormality, or other medical condition or situation occurs such that continued participation in the study would not be in the best interest of the subject (if there is reasonable evidence of clinical benefit to justify continuation on the protocol, this must be discussed with the Ophirex medical monitor)
- If the subject meets an exclusion criterion (either newly developed or not previously recognized) that precludes further study participation

If a clinically significant finding is identified (including, but not limited to, changes from Baseline) after enrollment, the Investigator or qualified designee will determine if any change in subject management is needed. Specifically, this includes withdrawal of subjects who were initially enrolled but whose history of chronic liver disease, renal laboratory tests, or pregnancy tests suggest they are subject to exclusion criteria 6, 7, or 10.

Discontinuation from IP does not mean discontinuation from the study, and remaining study procedures should be completed as indicated by the study protocol.

Section 14.6 describes procedures in the event of suspension or termination of the study for all subjects.

